7. COUNTRIES INVOLVED

The survey will be conducted among healthcare professionals mainly from the eight European countries represented in the SERENITY consortium:

- Denmark
- France
- Germany
- Italy
- The Netherlands
- Poland
- Spain
- United Kingdom

Due to promotion of the project via international networks and social media (s. section 10), we also expect participants from other countries and regions. Depending on the number or proportion of participants from outside Europe, these will be evaluated separately.

8. (TARGETED) NUMBER OF SUBJECTS

The study aims to generate data from a total of at least 800 healthcare professionals (i.e., either 100 each from the countries listed in section 7 or corresponding participant numbers from additional countries) and up to 2400 anonymised patients, considering that each healthcare professional will be asked to describe actual decisions and anonymous data obtained from medical charts in one to three consecutive patients meeting the definitions below at the time of consideration.

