10. DESCRIPTION OF STUDY PROCEDURES

The study will be divided into three phases: the recruitment phase, the FMR-phase and the data analysis phase.

In the **recruitment phase**, the national coordinators of the project group will advertise the study through traditional professional networks as well as their social media channels. Information about the study will be distributed via personal communication, relevant scientific organisations and journals, and via social media. The healthcare professionals of interest will be invited to pre-register for study participation so they can be assigned a unique link to the electronic case report forms (eCRF). During the preregistration, characteristics of the pre-registrants will be checked (i.e., sex, age, profession, years of experience, the country where they are practicing, and the number of cancer patients in palliative care whom they care for on a yearly basis).

In the **FMR phase**, all preregistered participants will be asked simultaneously to complete the survey using the *Castor electronic data capture platform* within seven days.

The survey will be divided into the following sections:

- a) **General questions** regarding end-of-life care (e.g., "When do you consider a patient in end-of-life care?") and (de)prescription of antithrombotic medication to cancer patients during end-of-life care (e.g., "Have you ever considered deprescribing antithrombotic medicine?").
- b) A sequence of **choice scenarios** i.e., hypothetical scenarios that vary with regard to several characteristics (**attributes**; e.g., bleeding risk, thrombotic risk). Attributes will be further specified by varying choice levels (**attribute levels**; e.g., low or high bleeding risk), which are considered relevant for the decision on continuation or stopping antithrombotic medication in the patient population studied. In accordance with the discrete choice experiment (DCE) methodology, participants will be asked to select the healthcare intervention (i.e., either continuation or discontinuation of the antithrombotic therapy) that in their opinion would benefit the patient the most within each choice set.
- c) Participants will be asked to share **actual case decisions** they made in a maximum of three consecutive cases involving patients with active cancer, who were considered to receive end-of-life care. Fully anonymised data of the patients (sex, age category, primary tumour, tumour

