15.4 Survey: Questions on actual case decisions

In the following (multiple choice) questions, you will be asked to describe one to three actual cases of patients with active cancer, who were considered to receive end-of-life care, in which you considered deprescription of antithrombotic medication.

1. Please select the age category of the patient (*< 40 years; 40-75 years; 75 years or older*)
2. Please indicate the type of antithrombotic medication involved (*DOAC; VKA; LMWH (therapeutic); antiplatelet agent*)
3. Please select the indication of the antithrombotic medication (*atrial fibrillation; treatment of acute VTE-event, prevention of (recurrent) VTE; mechanical heart valves; other indication (free text)*)
4. Please indicate the patient's performance status (*ECOG-PS grade 0-2, ECOG-PS ≥ 3*)
5. Please indicate the estimated prognosis of the patient at the time of consideration (*< 6 months; < 3 months; < 2 weeks*)
6. Please specify the setting of the patient at the time of consideration (*at home without palliative care; at home with palliative care; at rehabilitation facility; at nursing facility; at hospice facility; in 'acute care' setting; other (free text)*).
7. Please select one or more of the attributes that played a role in your consideration of deprescribing the antithrombotic medication; multiple answers are possible (*type of antithrombotic medication; indication of the antithrombotic medication; bleeding risk; thrombotic risk; sex; age; patient's performance status; patient's preference; other (free text)*).
8. Did you decide to deprescribe the antithrombotic treatment? (*yes; no*)

9. If no:

Which of the following attributes made you decide not to deprescribe the antithrombotic drugs? Multiple choices are possible.

Experience with deprescribing: not enough; enough

Symptom burden: high

Burden of medication (administration): low

Thrombotic risk: high

Bleeding risk: low

Antithrombotic medication indication: atrial fibrillation; acute VTE-event, prevention of (recurrent) VTE; mechanical heart valves; other indication (free text)

Sex: male; female, other (selection to be made)

Age: (< 40 years; 40-64 years; 65-74 years; 75 years or older)

Patient's performance status: ECOG-PS 0-2

Patient's prognosis: < 2 weeks; < 3 months; < 6 months (selection to be made)

Patient's preference: continue antithrombotic treatment

Other (free text)

10. If yes:

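### The case form has no answer for cases in which the respondent reached no decision, so a 'no' to Q8 can mix them with deliberate continuation

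*Combined protocol and SAP*

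**What the plan says.** The documents describe the unit of the case data in two ways.

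- **Decisions.** Section 10(c) asks participants for case decisions "they made in a maximum of three consecutive cases involving patients with active cancer". Section 8 says that "each healthcare professional will be asked to describe actual decisions and anonymous data obtained from medical charts in one to three consecutive patients", giving "up to 2400 anonymised patients". The heading of section 15.4 also speaks of decisions.
- **Considerations.** The lead-in under that heading asks for cases "in which you considered deprescription of antithrombotic medication". It does not require that a decision followed.

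The only outcome item on the form is Q8: "Did you decide to deprescribe the antithrombotic treatment", answered yes or no. A no leads to Q9: "Which of the following attributes made you decide not to deprescribe the antithrombotic drugs". Most of Q9's entries are worded as grounds for continuing, for example "Patient's preference: continue antithrombotic treatment". The list ends with a free-text entry. A yes leads to Q10, which asks for reasons for stopping.

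Section 13 says that the flash mob analysis is descriptive, with 95% confidence intervals. It does not say how Q8 is coded, which denominator is used, or how Q9 free text is handled. The documents do not say whether Q8 is mandatory.

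**The concern.** A case can meet the lead-in without containing a decision by the respondent: the patient died before one was made, the question was still open, or it was left to another prescriber. For such a case no is a truthful answer to Q8, and Q9 then asks for the reasons behind a decision that this respondent did not take.

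Two results are exposed. The Q9 tabulation is meant to show why clinicians continue treatment, and it could include cases in which nobody chose to continue. The share stopped would also be too low if it is reported as a share of decisions made, which is how section 10(c) describes the data. The two groups could not be reliably separated afterwards, because the patient data are anonymous and, under section 11, exported apart from the rest of the survey.

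**Working it through.** **The plan's own figure.** Section 8: 8 countries × 100 = 800 professionals, and 800 × 3 = 2400 cases. Both reproduce. The point does not rest on them; they only set the largest denominator for Q8.

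**The texts side by side.** The form itself treats considering and deciding as separable. Q5 and Q6 of 15.4 are dated to the consideration, and Q8 asks about the decision. In 15.2, Q5 and Q6 count considered and carried-out deprescribing separately. Section 8 asks for decisions but fixes patient eligibility at the time of consideration. Cases are also meant to be consecutive. A respondent who leaves out an undecided case breaks the sequence, and one who enters it has no fitting answer. No instruction says which to do.

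**Inputs for the illustration.** None of these is given in the documents; all are assumptions.

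- p: share stopped among decided cases, taken as 0.50 (range 0.2 to 0.7).
- u: share of entered cases with no decision by the respondent, taken as 5%, 10% and 20% (range 2% to 30%).
- All undecided cases are entered and answered no.

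**Formulas.** Observed share answering yes = p(1 − u). Difference from the share among decided cases = −p·u. Share of no answers that are not decisions = u / [u + (1 − u)(1 − p)].

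| u | Observed share, p = 0.50 | Difference from p | Non-decisions among the no answers |
|---|---|---|---|
| 5% | 0.50 × 0.95 = 47.5% | −2.5 points | 0.05 / 0.525 = 9.5% |
| 10% | 0.50 × 0.90 = 45.0% | −5.0 points | 0.10 / 0.55 = 18.2% |
| 20% | 0.50 × 0.80 = 40.0% | −10.0 points | 0.20 / 0.60 = 33.3% |

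Over the wider ranges the difference runs from 0.2 × 0.02 = 0.4 points to 0.7 × 0.30 = 21 points.

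**Against the planned precision.** At u = 5% and 2400 cases the 95% half-width is 1.96 × √(0.475 × 0.525 / 2400) = 2.0 points, against a difference of 2.5. At p = 0.50 the difference passes the half-width once u is about 4% with 2400 cases, or about 7% with 800. These half-widths ignore clustering of up to three cases per respondent. Allowing for it would widen the intervals and raise both thresholds.

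**Which share is affected.** If the target is the share of all considered cases that the respondent decided to stop, p(1 − u) is that share and there is no bias. A case that stayed open, or in which the patient died first, did not end in a decision to stop. The exception is a case left to another prescriber who then stopped the drug: treatment ended, but Q8 is truthfully no. The Q9 problem remains under either target.

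**The case against.** The strongest reply is that undecided cases do not belong in the data. The section heading, section 8 and section 10(c) all ask for actual decisions, and Q13 treats consideration and decision as one moment. A respondent with nothing decided may simply leave the case out. This stands as far as it goes: a reader might infer from the lead-in that every considered case is admitted, and the wider text does not support that. But then the lead-in contradicts the body, and one of them has to change.

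Second, a reader might infer that undecided cases are scored as decisions to continue. No scoring rule exists. Q8 may be skippable, and Q9's free text could identify some of these cases. What stands is that the form allows the mixing and that no rule is given to undo it.

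Third, the plan does not name the share stopped as its main case-level result; it promises only description. The loss against p is a bias only for the share among decided cases. That is correct, and it limits the claim about the share. It does not clear the Q9 reasons.

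Fourth, the signs that such cases occur are indirect. A prognosis under two weeks in Q5 makes death before a decision possible but does not show it. Discussing a case with colleagues (15.2 Q7) is not handing over the decision. The seven-day entry window does not show that decisions were still open, since cases are described in retrospect. Section 6 recruits some professionals who may not hold the prescription, but nothing shows that they would enter cases they did not decide. All of this stands, and it is why no size can be claimed.

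**Conclusion.** The missing category is real and can be read directly from 15.4: a lead-in based on consideration, a two-way Q8, and a Q9 that words every no as a choice. It can contaminate the Q9 reasons, and it lowers the share stopped if that share is read as one of decisions made.

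Its size is unknown. The figures of 47.5% down to 40%, and 9.5% up to 33% of the cases answering Q9, hold only for p = 0.50, u of 5% to 20%, and every undecided case being entered as no. Under other assumed values the loss could be well under one point.

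A reader might go further and conclude that comparisons between professions are distorted, because some hold the prescription less often. The documents name no such comparison and give no undecided share for any profession, so that remains hypothetical. This is an inexpensive improvement to the form and its reporting. It does not show that the case results would be wrong.

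**What to change.** 1. Add a third answer to Q8: *no decision reached by me (patient died first / still open / left to another prescriber)*. Route it past Q9 and Q10.
2. Reconcile the 15.4 lead-in with section 10(c), so that respondents know whether a consecutive case without a decision is to be entered.
3. In section 13, report the number of no-decision cases, and give the share stopped both among decided cases (yes + no) and among all considered cases.

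The cost is one answer option and one skip in the eCRF, plus a short addition to section 13. The decided-case share has a somewhat smaller denominator: at an assumed u of 10%, 2400 × 0.90 = 2160 cases instead of 2400. Reporting both shares means that the choice of denominator need not be settled in advance.

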Which of the following attributes made you decide to deprescribe the antithrombotic drugs?

Multiple choices are possible.

Experience with deprescribing: enough

Symptom burden: low

Burden of medication (administration): high

Thrombotic risk: low

Bleeding risk: high

Antithrombotic medication indication: atrial fibrillation; acute VTE-event, prevention of (recurrent) VTE; mechanical heart valves; other indication (free text)

Sex: male; female, other (selection to be made)

Age: (< 40 years; 40-64 years; 65-74 years; 75 years or older)

Patient's performance status: ECOG-PS grade ≥ 3

Patient's prognosis: < 2 weeks; < 3 months; < 6 months (selection to be made)

Patient's preference: stop antithrombotic treatment

Other (free text)

Tumour-specific

11. Please select the type of cancer (*breast; lung; upper gastro-intestinal (GI); lower GI; endocrine; genito-urinary tract; brain; haematological; skin (excluding squamous/basal cell carcinoma); combination (select more than one); other (free text)*)
12. Please select the stage of cancer (*localized; regional; distant metastasis; not applicable*)
13. Please select the cancer treatment at the time of consideration/decision – multiple options possible (*none; surgery (in the previous 3 months); radiation therapy (in the previous month); chemotherapy (in the previous month); immunotherapy (in the previous month)*)
14. Please select the line of cancer treatment (*first-line, second-line, third-line, fourth-line, not applicable*)

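### The coded answers on symptom burden allow only high as a reason for continuing and only low as a reason for stopping, and the term is undefined, so the form sets the coded direction

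*Combined protocol and SAP*

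**What the plan says.** Section 15.4 of the combined protocol and SAP collects one to three real cases per respondent. Question 8 records whether treatment was stopped, and the answer decides which list of reasons follows.

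- **Not stopped, question 9:** "Which of the following attributes made you decide not to deprescribe the antithrombotic drugs". The symptom line reads "Symptom burden: high".
- **Stopped, question 10:** "Which of the following attributes made you decide to deprescribe the antithrombotic drugs". The symptom line reads "Symptom burden: low".

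Each list has 12 lines, allows several ticks and ends with a free-text line. Some lines leave the level to the respondent in both lists, for example "Patient's prognosis: < 2 weeks; < 3 months; < 6 months (selection to be made". One line offers two levels in question 9 only: "Experience with deprescribing: not enough; enough".

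Question 7, asked before the decision is recorded, lists the attributes that played a role: "type of antithrombotic medication; indication of the antithrombotic medication; bleeding risk; thrombotic risk; sex; age; patient's performance status; patient's preference; other (free text". Symptom burden is not among them. It is also absent from the factor list in section 15.2.1 and from the example scenarios in section 15.3. Section 13 plans a descriptive main analysis of the flash mob data with 95% confidence intervals.

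**The concern.** A descriptive study should let the answers show which way a factor worked. Here each decision comes with one preset level of symptom burden. A table of the coded answers will show low burden in every stopped case that carries a tick and high burden in every continued case that carries one. A reader could take that for a finding about practice, although the form produced it.

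The missing definition adds a second problem. If one respondent thinks of cancer symptoms and another of symptoms of thrombosis, their ticks do not mean the same thing and cannot safely be added up.

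The first objective in section 4 is to describe current practice, and section 3 presents the results as a first step towards a clinical decision tool. A direction that comes from the form should not be carried into that tool.

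**Working it through.** The plan states no figure for this item, so there is none to reproduce. The check sets the answer options side by side and then illustrates their effect.

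**1. Coded options by decision and level**

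| Decision (question 8) | Burden high | Burden low |
|---|---|---|
| Not stopped (question 9) | coded | no code |
| Stopped (question 10) | no code | coded |

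Two of four cells are zero by construction. This needs no assumption.

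**2. Can the level be recovered elsewhere?** Performance status is also one-sided in questions 9 and 10, but question 4 records it for every case. Symptom burden is not recorded in questions 1 to 7 or 11 to 14.

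**3. Do the neighbouring lines settle the meaning?** They do not.
- If symptoms of thrombosis are meant, high burden in question 9 sits naturally beside high thrombotic risk in the same list.
- If overall cancer symptoms are meant, question 9 lists high burden beside the better performance status (grade 0-2), and question 10 lists low burden beside the worse one (grade 3 or above).
- The medication-burden line runs the other way: low in question 9, and "Burden of medication (administration): high" in question 10.

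The protocol gives no rationale for the pairing.

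**4. Illustration.** Section 8 gives the ceiling: 800 respondents × 3 cases = 2400. The other inputs are assumptions, not document figures: 50% of cases have high burden; burden is a reason in 40% of cases, independently of level and decision; the level cited is the patient's level; free text is not counted as coded. With s_H and s_L the probabilities of stopping at high and low burden, the expected share of burden-related reasons without a code is

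0.5 × s_H + 0.5 × (1 − s_L).

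The 40% cancels. One simulated run per scenario gave:

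| s_H / s_L | Stop-high | Stop-low | Continue-high | Continue-low | Without a code | Expected |
|---|---|---|---|---|---|---|
| 0.7 / 0.3 | 349 | 147 | 161 | 331 | (349+331)/988 = 69% | 0.35+0.35 = 70% |
| 0.5 / 0.5 | 238 | 252 | 249 | 245 | (238+245)/984 = 49% | 0.25+0.25 = 50% |
| 0.3 / 0.7 | 126 | 345 | 338 | 138 | (126+138)/947 = 28% | 0.15+0.15 = 30% |

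**5. What each form would show.** With both levels available under both decisions, the share of high burden among stopped against continued cases would be:
- first scenario: 349/496 = 70% against 161/492 = 33%;
- second scenario: 238/490 = 49% against 249/494 = 50%;
- third scenario: 126/471 = 27% against 338/476 = 71%.

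The direction follows the data. With the form as written, the coded shares are 0% against 100% in all three scenarios.

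**The case against.** The strongest reply is that questions 9 and 10 are checklists of reasons, not measurements. They ask what drove the decision, and a directional list of reasons is a recognisable format. Medication burden, thrombotic risk, bleeding risk, performance status and patient preference are one-sided too. No cross-tabulation of level by decision is planned, and how often each reason is ticked remains usable.

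Much of this stands. One-sidedness alone does not single out this item. What does is that the term has no definition, its expected direction is not evident from the lists, and its level is recorded nowhere. For bleeding or thrombotic risk the intended meaning is at least clear. Reading the list as presumed reasons also concedes that the direction is an input from the designers, so it cannot be reported as a result.

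Some stronger readings are tempting, but the documents do not support them:

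- **That a respondent with the opposite reason has no answer at all.** Both lists end with free text. The gap is the lack of a code and of a recoding rule.
- **That questions 9 and 10 contradict each other.** They mirror each other. Medication burden is a different construct, so its opposite direction is no inconsistency. A transposition cannot be ruled out, but it is not shown.
- **That all 2400 cases are compromised.** That number is a ceiling on cases, not a count of those affected.

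**Conclusion.** The concern holds for the coded options. High burden can be coded only for continuing and low burden only for stopping, so the coded direction carries no information. Tick frequency does, subject to the doubt about what each tick means.

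The missing options affect only cases in which symptom burden was a reason in the unlisted direction. The documents give no rate for this. The 28% to 69% in the illustration applies to burden-related reasons under assumed inputs; it shows how the form behaves and is not an estimate for this study. The missing definition bears on the ticks that are made.

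A reader might also infer that the preference coefficients are biased. They are not touched: they come from the choice scenarios, and symptom burden does not appear in the examples given in section 15.3. This is one line of 12 in a descriptive section. It should be corrected, but it does not threaten the study as a whole.

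**What to change.** **Before launch**
- State which symptoms are meant.
- In both question 9 and question 10, offer low and high and let the respondent select, as the prognosis line already does.
- Have the sponsor confirm the intended direction of the current pairing.
- Write down how free-text reasons will be recoded.
- Optionally, record the level of symptom burden once for each case before question 8, so that the patient's state and the clinician's reason are separate.

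The cost is one or two extra survey lines per case, repeated for up to three cases. No additional participants are needed.

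**If data are already collected** (section 12 schedules this for May 2023)
- Report the item as tick frequency only.
- Recode the free text by a stated rule.
- Draw no conclusion about the direction of the association between symptom burden and deprescribing, and state the limitation. The missing levels cannot be recovered from the anonymised cases.

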2. DEFINITIONS

2.1 Active cancer

Cancer diagnosed within the previous six months; recurrent, regionally advanced or metastatic cancer; cancer for which treatment has been administered within the past six months; or haematological cancer that is not in complete remission. Basal cell or squamous cell carcinoma of the skin are excluded from this definition.

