3. BACKGROUND

Deprescribing (i.e., discontinuing medication) is an important part of palliative care to prevent polypharmacy, which is associated with increased risk of adverse drug events, drug-drug and drug-disease interactions, reduced functional capacity, multiple geriatric syndromes, medication nonadherence, and higher healthcare costs. One of the most widely used cardiovascular drug classes in cancer patients in a palliative setting are antithrombotics, including anticoagulant and anti-platelet agents. Antithrombotic drugs, e.g., (DOACs), low-molecular-weight heparins (LMWH), vitamin-K antagonists (VKA) and so-called antiplatelet agents (such as acetyl salicylic acid and P2Y12 inhibitors), are indicated in patients with prosthetic heart valves, in those with venous thromboembolism (VTE), for stroke prevention in atrial fibrillation as well as in patients with established atherosclerotic cardiovascular disease (such as myocardial infarction, stroke, or peripheral artery disease). Most patients have been receiving these drugs chronically before their cancer was diagnosed, whilst others are being prescribed them in order to treat or prevent cancer-associated thrombosis. Obviously, decisions on deprescribing antithrombotics heavily depend on the indication of the antithrombotic drug in addition to patient and healthcare professional preferences and experience, and on the estimated life expectancy of the patient.

Understanding current patterns of management of antithrombotic therapy (ATT) as well as the rationale and preferences behind these patterns is crucial for improving clinical practice. Since deprescribing patterns and rationale may largely differ across countries, relevant data at a large scale is needed to fully understand and appreciate the relevant decision processes.

The insights gained in this study are a first step towards the development of a clinical decision tool supporting decisions on ATT in cancer patients.

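### Question 13 of the case survey (section 15.4) is a closed list without endocrine, targeted or 'other' options, so some treated cases have no correct answer

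*Combined protocol and SAP*

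**What the plan says.** Section 15.4 asks each respondent to describe one to three "actual cases of patients with active cancer, who were considered to receive end-of-life care". Question 13 begins "Please select the cancer treatment at the time of consideration/decision" and allows several answers. There are five options: 'none'; "surgery (in the previous 3 months); radiation therapy (in the previous month"; and "chemotherapy (in the previous month); immunotherapy (in the previous month".

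The list ends there. By contrast, question 11 on tumour type closes with "combination (select more than one); other (free text", and questions 3, 6, 7, 9 and 10 also offer a free-text 'other'. Question 14 asks for the line of treatment, with a 'not applicable' answer, but for neither drug class nor timing. No instruction says how an unlisted treatment should be entered, or whether question 13 must be answered.

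Section 2.1 defines active cancer by several alternative routes. One is "cancer for which treatment has been administered within the past six months". Others include "Cancer diagnosed within the previous six months; recurrent, regionally advanced or metastatic cancer".

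**The concern.** A closed list works when it is exhaustive. Question 13 is not: it names two systemic classes and gives no place for any other. A respondent whose patient is on endocrine or targeted therapy alone must improvise, and respondents from eleven professions and at least eight countries will not all improvise in the same way.

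Question 13 is the only item that records the type of concurrent cancer treatment. If its coding varies by respondent, the reported distribution of treatment does not mean what its labels say, and neither does a table of continue-or-stop decisions by treatment. Without a free-text field the analyst cannot detect the problem. Repair afterwards is also unlikely: the patient data are anonymised (sections 10 and 11), collection lasts seven days (section 12), and the plan describes no route for querying an entry.

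**Working it through.** The plan gives no figure to reproduce here. The check is a comparison of the option list with the cases it has to classify.

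**Step 1: what question 13 can record.**

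| Situation at the decision | Correct answer available? |
|---|---|
| Chemotherapy three weeks ago | Yes: chemotherapy |
| Chemotherapy ended four months ago, nothing since | Yes: 'none' fits the question as asked |
| Endocrine therapy only, ongoing | No |
| Targeted therapy only, ongoing | No |
| Chemotherapy plus an unlisted class | In part: the unlisted class is lost |

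The third and fourth rows are the defect.

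**Step 2: where such a case can go, and what each choice does.**

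- 'None': a treated case enters the untreated group.
- Nearest listed class: treated versus untreated is preserved, but the split between drug classes is wrong.
- Blank: the item is missing for a reason related to treatment.

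The documents do not say which choice is expected, so the likely result is a mixture that varies by respondent.

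**Step 3: can question 14 recover the information?** Only in part. 'None' at question 13 with, say, second-line at question 14 could be a patient on an unlisted drug now, or one whose second-line treatment stopped long ago. With no class and no time window in question 14, the two look identical.

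**Step 4: do the look-back periods conflict with section 2.1?** Radiation, chemotherapy and immunotherapy are covered for 1 of the 6 months and surgery for 3 of the 6. However, section 2.1 decides who is eligible, by several alternative routes, while question 13 describes treatment around the decision. The two serve different purposes and can both be right. The remaining limitation is modest: question 13 cannot show whether a patient met the six-month treatment route.

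**Step 5: size.** The upper limit of case records is 800 × 3 = 2400 (section 8). If a share *u* of cases were on an unlisted treatment only, *u* × 2400 records would have no correct option. The documents give no value for *u*. Over an assumed range:

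- *u* = 5%: 0.05 × 2400 = 120
- *u* = 10%: 0.10 × 2400 = 240
- *u* = 20%: 0.20 × 2400 = 480

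These figures show scale only and are not estimates.

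**The case against.** The strongest reply is that little depends on this item. Section 13 is descriptive and names no comparison by cancer treatment. Treatment is not among the patient data listed in section 10, not among the example factors in 15.2.1, not a listed factor in questions 7, 9 or 10, and not an attribute in the example choice scenarios of 15.3. If cancer therapy drove a decision, the free-text fields of questions 7, 9 and 10 could record it. The Background's mention of "increased risk of adverse drug events, drug-drug and drug-disease interactions" concerns polypharmacy in general and sets no aim of studying interactions with anticancer drugs. Questions 2, 4, 5 and 12 have no 'other' either.

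Most of this stands, and it limits the importance of the point. It does not remove it. An item that is collected will presumably be tabulated, and the free-text fields elsewhere record reasons for a decision, not treatment status. Lacking an 'other' is harmless where the options cover every case, as with the two performance-status bands of question 4. In question 13 they do not.

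A reader might go further in two ways that the documents do not support:

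- **That the one- and three-month periods contradict the six-month definition.** They do not, for the reason in step 4. 'None' can be the right answer for chemotherapy that ended two to six months earlier.
- **That treated patients are always recorded as 'none', diluting a treated-versus-untreated contrast by a calculable amount.** 'None' is only one of three possible entries. A dilution figure would need the misfiled share, the true difference, and the assumption that misfiled cases are stopped at the same rate as other treated cases. The documents supply none of these.

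**Conclusion.** The point holds in a limited form. Question 13 has no correct answer for a case whose only current cancer treatment is endocrine, targeted or another unlisted class, and such cases will probably be coded inconsistently. The gap itself is plain from the option list. The inconsistency is an inference from the absence of any coding instruction. It also assumes that some reported cases are on such treatments, which the documents neither state nor exclude.

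The consequence is an unreliable distribution of concurrent cancer treatment and unreliable descriptions of case decisions by it. The size cannot be computed from the documents. The general questions, the choice experiment and the other case items are not affected. The change is worth making because it is nearly free before launch, and the lost information is unlikely to be recoverable afterwards.

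**What to change.** Before launch, change the answer options of question 13 in section 15.4 and the eCRF:

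- Add 'endocrine therapy (in the previous month)', 'targeted therapy (in the previous month)' and 'other (free text)'.
- Relabel 'none' as 'none of these within the stated periods', and make it mutually exclusive with every other option.

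The relabelling makes clear that 'none' refers to the listed look-back periods and not to treatment history as a whole. Splitting 'none' by treatment within six months is not advised: the extra category would overlap with the existing look-back options, since a patient who finished chemotherapy three weeks ago would fit both.

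The cost is three more answer categories, some likely to have small counts, plus some free text to classify. No question is added. If collection has already closed, the remaining remedy is to report question 13 with this limitation stated and not to interpret its 'none' group as untreated.
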